#### **HIV-uninfected individuals**

1. Confirmed HIV-1 infection
2. At high risk of severe COVID-19 disease as defined by one of the following:
  - History of hypertension, atherosclerotic cardiovascular disease (ASCVD), coronary artery disease, diabetes mellitus
  - History of asthma or chronic pulmonary disease
  - History of renal disease and chronic renal insufficiency
  - BMI over 35
3. Any acute or chronic medical condition that in the opinion of the investigator would preclude participation
4. Chronic autoimmune disease
5. Active IV drug use
6. Excessive use of alcohol or recreational drugs that in the opinion of the investigator would preclude participation
7. Decompensated psychiatric illness
8. Need for chronic immunotherapy including systemic corticosteroids, other MAb therapy, or immunosuppressive drugs
9. Volunteers born female who are pregnant, lactating, or planning on becoming pregnant over the study period
10. Any of the following laboratory parameters:
  - Hemoglobin <10.0 g/dL
  - Absolute neutrophil count <1,000/mm^3
  - Absolute lymphocyte count <500/mm^3
  - Platelet count <100,000/mm^3
  - Creatinine >1.25x upper limit of normal (ULN)
  - Aspartate aminotransferase (AST) >1.5x ULN
  - Alanine aminotransferase (ALT) >1.5x ULN
  - Glucose (non-fasting) >160 mg/dL
  - Proteinuria: 2+ or greater
  - Hematuria: >10 red blood cells (RBCs) per high-power field

11. Previous receipt of an experimental MAb for HIV-1 treatment or prevention in a research study
12. History of severe allergic reactions to drugs, vaccines, or drug infusion
13. Participation in another investigational clinical trial within the past 12 weeks or anticipated during the course of the current study
14. History of coagulopathy that would preclude administration of IM injections (IM Group only)
15. Skin rashes or tattoos that would prevent ability to assess IM injection for injection-site reactions (IM Group only)
16. Use of high-dose aspirin, clopidogrel, prasugrel, ticagrelor, dipyridamole or any other antiplatelet medication that would interfere with the ability to receive IM injections (IM Group only).

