## 7. Study Assessments

A central laboratory will analyze all blood and urine samples with the exception of the HIV-1 resistance testing, immunogenicity testing, and PK assessments, which will be undertaken by appropriate specialty contract laboratories. Urine samples will be analyzed at the site; if abnormal results are obtained for a subject, a urine sample will be sent to the central laboratory for microscopic evaluation.

The following assessments will be conducted at the times indicated in the Schedules of Events ([Table 1](#), [Table 2](#), [Table 3](#), and [Table 4](#)).

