## 7.2 Blood and Urine Samples

### 7.2.1 Clinical Laboratory Parameters

Collection of blood and urine samples for clinical laboratory assessments will be part of the safety profile assessment for the study subjects. Subjects do not need to fast before blood sampling. Samples will be processed using standard procedures as described in the laboratory procedures manual and will be analyzed by a central laboratory unless otherwise noted.

The samples will be analyzed for the following:

- **Hematology:** complete white blood cell count with differential, hemoglobin, hematocrit, and platelets. Prothrombin time and partial thromboplastin time will also be collected at Screening only for the IM group.

- **Serum chemistry profile:** albumin, alkaline phosphatase, ALT, amylase, AST, blood urea nitrogen, calcium, chloride, creatine phosphokinase, creatinine, direct bilirubin, gamma glutamyl transferase, glucose, lactate dehydrogenase, magnesium, phosphorus, potassium, sodium, total bilirubin, total protein, and uric acid.
- **Urinalysis:** visual inspection for appearance and dipstick assessment for color, pH, specific gravity, ketones, protein, glucose, bilirubin, nitrite, urobilinogen, and leukocyte esterase.

The urinalysis will be performed at the site by qualified personnel. If the results of the urinalysis are abnormal, a urine sample will be sent to the central laboratory for microscopic evaluation. Samples will be processed as described in the laboratory procedures manual before being sent to the central laboratory for evaluation.

Tests with Grade 3 or Grade 4 abnormal results should be repeated within 72 hours of the site becoming aware of the abnormal value(s) with the exception of CD4+ T cell levels. See [Appendix B](#) for details and definitions of toxicities. The investigator should discuss any Grade 3 or 4 abnormal laboratory results with the medical monitor/Sponsor for appropriate subject disposition, including potential withdrawal from the study. Refer to [Section 4.3](#) (Safety Monitoring and Toxicity Management Plan) for information on DMC reporting and subject discontinuation in the event of study drug-related AEs.

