### **9.5.2 Clinical Safety Laboratory Parameters**

Clinical laboratory parameters will be presented by visit. Descriptive statistics will be used to summarize observed values by visit as well as the change from baseline at each visit. Clinical laboratory values outside the normal ranges will be flagged in subject data listings. Non-numeric data will be presented in subject data listings but will not be tabulated.

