#### Safety Assessments

Safety assessments will include the following through End of Study for each Group:

- Physical examinations
- Vital sign measurements
- Clinical laboratory parameters (hematology, serum chemistry, urinalysis and CD4+ T-cell count)
- Monitoring of AEs and concomitant medications
- Anti-Trogarzo® antibody levels (immunogenicity of Trogarzo®)
- Injection site reactions in subjects receiving Trogarzo® IM

Laboratory samples will be collected every two weeks, at visits where Trogarzo® is administered. Beginning at Day 29 (4 weeks), non-laboratory safety assessments will be performed as scheduled through Day 99 (14 weeks) for the IM HIV uninfected Group, and through Day 85 (12 weeks) for the IM HIV infected Group.

The figure below illustrates the Analysis Phases and Periods to be utilized.

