#### **4.3.3. Clinical Laboratory Parameters**

Summary statistics will be presented for laboratory measurements overall for all subjects in the SAF Population. The following analytes will be tabulated/listed:

- **Hematology:** complete white blood cell count with differential, hemoglobin, hematocrit, and platelets.

- **Serum chemistry profile:** albumin, alkaline phosphatase, alanine aminotransferase (ALT), amylase, aspartate aminotransferase (AST), blood urea nitrogen, calcium, chloride, creatine phosphokinase, creatinine, direct bilirubin, gamma glutamyl transferase, glucose, lactate dehydrogenase magnesium, phosphorus, potassium, sodium, total bilirubin, total protein, and uric acid. In addition, eGFR will be presented using the following formula:  $eGFR = 1.86 \times [Creatinine/88.4]^{-1.154} \times [Age]^{-0.203} \times [0.742 \text{ if female}] \times [1.210 \text{ if Black}]$ .
- **CD4+ Cell Counts**

Urinalysis results will be presented in a data listing and will include results from microscopic testing only. Pregnancy test, Serum Follicle-Stimulating Hormone (FSH) test, Hepatitis Serology, C-reactive Protein, Prothrombin Time and Partial Thromboplastin Time, and Viral Resistance Testing will also be presented in data listings only.

Normal ranges for the laboratory parameters will be provided by the laboratory that performed the assessments. All normal ranges will be standardized and results will be reported in standard units. The tables will include summary statistics for the assessments and the changes from Baseline to each subsequent time point of measurement. A table of subjects with abnormal (i.e., outside normal range) laboratory assessments will also be presented as a frequency of the incidence of each DAIDS toxicity grade (1 – 4) and route of administration.

Potentially Clinically Significant (PCS) criteria may be applied to laboratory parameters as clinically indicated, and if applied, will be summarized as described above. PCS is defined as a laboratory value that is lower or higher than a laboratory's normal range limits.

Note: Electronic clinical laboratory data will be received at Westat. Data reconciliation will be performed to resolve any discrepancies with the Oracle database. Details of data receipt will be described in the Data Receipt Plan.

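### Both SAPs limit the urinalysis listing to follow-on microscopy, so no planned output carries the scheduled dipstick results, including urine protein and glucose

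*SAP*

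**What the plan says.** **What is collected.** Protocol Section 7.2.1 defines the urinalysis as "visual inspection for appearance and dipstick assessment for color, pH, specific gravity, ketones, protein, glucose, bilirubin, nitrite, urobilinogen, and leukocyte esterase". It is done at the site, and its purpose is stated in the same section: "Collection of blood and urine samples for clinical laboratory assessments will be part of the safety profile assessment for the study subjects".

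**When microscopy is done.** It depends on the site result: "If the results of the urinalysis are abnormal, a urine sample will be sent to the central laboratory for microscopic evaluation". The opening of protocol Section 7 gives the same rule.

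**What is reported.** Section 4.3.3 of the IM SAP and Section 4.3.3 of the IV push SAP contain the same sentence: "Urinalysis results will be presented in a data listing and will include results from microscopic testing only". The Safety Assessments part of the IM SAP nevertheless names urinalysis among the safety laboratory parameters ("hematology, serum chemistry, urinalysis and CD4").

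**The general reporting rule.** Protocol Section 9.5.2 has clinical laboratory parameters presented by visit and out-of-range values flagged in listings. It adds: "Non-numeric data will be presented in subject data listings but will not be tabulated". Section 4.3 of both SAPs repeats the flagging rule and the rule that non-numeric data are listed but not summarised.

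**The concern.** The SAPs keep the conditional follow-up test and leave out the scheduled one. Dipstick protein and glucose are mostly graded, non-numeric results, and the plan says that such results go into listings. Under the microscopy-only sentence they go nowhere.

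Safety of push and IM administration is a primary objective, and urinalysis is one of the assessments meant to serve it. The protocol also treats urine protein as relevant at entry: HIV-uninfected volunteers are excluded for "Proteinuria: 2+ or greater" (Section 5.2). Urine protein is measured only on the dipstick, so even the screening value behind that criterion would be absent from the planned outputs. A reader of the report could not follow urine protein or glucose in a subject from infusion into the push or IM period.

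**Working it through.** The plan gives no figure to reproduce. The check sets the texts side by side and then counts the results affected.

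**Step 1. Is there another planned output for dipstick results?**

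- Section 4.3.3 of each SAP names hematology, serum chemistry and CD4+ counts as the analytes to be tabulated or listed. Urinalysis gets its own sentence, limited to microscopy.
- The mock abnormal-laboratory listings (IM Listing 16.2.8.5, IV push Listing 16.2.7.1.5) show only chemistry and hematology categories.
- The IV push mock urinalysis listing (16.2.7.1.3) shows crystals, casts, mucous threads and sediment. The IM mock (16.2.8.3) has placeholders only. Mock contents are examples, so this is support rather than proof.
- The IM tables by DAIDS grade and route (14.3.2.1 and 14.3.2.2) have placeholder analytes and name no urine test.
- A programming note asks that each listing include all applicable data. It does not override a sentence that says which data apply.

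No table or listing is assigned to dipstick results.

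**Step 2. What survives and what does not?** Take an HIV-uninfected volunteer with 2+ protein on the Day 57 dipstick and clear microscopy.

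| Information | In planned outputs? |
|---|---|
| A urine sample went to microscopy at Day 57 | Yes, as a microscopy row, from which an abnormal site result can be inferred |
| The abnormal item was protein | No |
| The level was 2+ | No |
| Dipstick protein at baseline (Day -55) and at other visits | No |
| Normal dipstick results, in this or any other subject | No |
| An adverse event, if the investigator judges the change clinically significant | Yes |

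**Step 3. How many scheduled urinalyses?** Counts are per completing subject, Screening included, from protocol Tables 1 to 4.

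- Sentinel: Screening and Days 1, 15, 29, 43, 57, 71, 85, 99 = 9.
- HIV-infected Core or IM: Screening and Days 1, 15, 29, 43, 57, 71, 85 = 8.
- HIV-uninfected Core or IM: Screening and Days -55, -41, -27, -13 (5), plus Days 1, 15, 29, 43, 57, 71, 85, 99 (8) = 13.

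Section 6.2 instead describes pre-steady-state blood and urine safety sampling every four weeks from Day -55. That leaves Screening, Day -55 and Day -27 before Day 1, so 3 + 8 = 11. Section 6.2 is written for the Core Group, while Table 2 covers both Core and IM.

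The documents do not fix the mix of infected and uninfected subjects, so each range runs from all infected to all uninfected:

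| Portion | Tables 1 to 4 | Four-weekly pre-steady-state sampling |
|---|---|---|
| IM (20 subjects) | 20 × 8 = 160 to 20 × 13 = 260 | 160 to 20 × 11 = 220 |
| Sentinel (5) and Core (15) | 45 + 15 × 8 = 165 to 45 + 15 × 13 = 240 | 165 to 45 + 15 × 11 = 210 |
| All | 325 to 500 | 325 to 430 |

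The columns of Table 4 are partly broken in the text available. The urinalysis row was read as above, which agrees with the two-weekly schedule in Section 6.3.

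**The case against.** The strongest reply is that little of clinical weight is hidden.

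- An abnormal dipstick triggers microscopy, and microscopy is listed by subject, visit and date, so the occurrence leaves a trace.
- Subjects with a microscopy row, over the Safety Population N, give a rough count of subjects with an abnormal urinalysis.
- The adverse event route is fairly broad. Protocol Section 8.3 counts a laboratory change as clinically significant if it needs action or if the investigator judges it beyond normal physiological fluctuation. New 2+ protein in a healthy volunteer could meet that. The DMC also discusses abnormal laboratory results (Section 8.8).
- Creatinine, blood urea nitrogen, albumin, total protein, serum glucose and eGFR are all reported.
- The prior-study summaries in protocol Section 1.2 report no proteinuria or glycosuria signal.

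Most of this stands, and it limits the point. A reader might infer that a subject with proteinuria would simply appear to have unremarkable urine, or that no denominator of any kind exists. The documents support neither: the microscopy row shows that something was abnormal, and the Safety Population N is available. What cannot be confirmed from the outputs is how many subjects had a dipstick at a given visit.

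The reply does not restore the item, its level, its baseline or the normal results. Serum tests are not urine tests. The adverse event route depends on individual judgement and does not report the measurement. Nor does the reply resolve the conflict between the microscopy-only sentence and protocol Section 9.5.2, for which neither SAP gives a reason.

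**Conclusion.** The point holds as a gap in the planned safety outputs. Section 4.3.3 of both SAPs leaves out every scheduled dipstick result, contrary to protocol Section 9.5.2 and to the listing rule in Section 4.3 of the SAPs themselves. Change in urine protein or glucose between IV infusion and push or IM cannot be seen.

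For the IM portion the size is about 160 to 260 scheduled urinalyses on Tables 2 and 4, or 160 to 220 on the four-weekly text. This assumes that 20 subjects complete and leaves the infected/uninfected mix open. The figures count omitted results and do not measure an effect on any conclusion. The PK bridging analyses are untouched.

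Two further readings go beyond the documents. One is that the data themselves are lost. Protocol Section 10.1 says that all data are entered in the EDC system, and the IM SAP addendum says that all collected data go into the submission package. Neither names dipstick values, so the claim here concerns tables and listings only. The other is that the plan owes a summary table of dipstick changes by route. It does not, because it says that non-numeric data are listed and not tabulated.

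**What to change.** In Section 4.3.3 of both SAPs, replace the microscopy-only limit with wording such as: *dipstick results at each scheduled visit and, where done, microscopic results, listed by subject, visit and period with abnormal values flagged*. Change IM Listing 16.2.8.3 and IV push Listing 16.2.7.1.3 to match. Both mocks already have visit, date, period, test, unit and result columns, so only an abnormal flag has to be added. A by-route table of worsening is not proposed, since it would run against the no-tabulation rule.

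The cost is one sentence in each SAP and a longer listing. At ten dipstick items per urinalysis, the IM listing would gain about 160 × 10 = 1,600 to 260 × 10 = 2,600 item results. No visit, sample or procedure is added. The low cost assumes that dipstick values are in the EDC system, as the general statement in Section 10.1 implies. This should be confirmed before the listing is programmed. Table 2 and Section 6.2 should also be reconciled on pre-steady-state urine sampling, so that the expected rows per subject are known.

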#### **4.3.4. Vital Signs**

Summary statistics for vital signs and weight will be presented overall for all subjects in the SAF Population for all scheduled visits. Actual values and changes from Baseline will be summarized for all visits where collected.

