### 7.1.4 Vital Sign Measurements

Vital sign measurements will include the subject’s heart rate (beats/minute), blood pressure (mm Hg), respiratory rate (breaths/minute), and oral temperature (°C). Measurements will be taken within 1 hour before the start of the study drug administration and again at both the beginning and end of the 15 minute (HIV-infected) or 60 minute (HIV-uninfected) post-administration observation period. Blood pressure and heart rate measurements will be obtained after the subject has been seated for at least 5 minutes. Ideally, each subject’s blood pressure should be measured using the same arm and the same size cuff at each visit.

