### **3. Statistical Analysis Considerations**

#### ***3.1. Sample Size***

Anticipated enrollment in the IM portion is 20 subjects from 4 sites in the United States.

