**3.3.3. Baseline Values**

Baseline is defined as the last assessment prior to the first dose of study drug (Day 1 for all HIV infected subjects, Day -55 for HIV uninfected subjects).

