**Listing 16.2.9**  
**Vital Signs**

Group	Subject ID	Visit	Visit Date	Scheduled Time Point	Time (hh:mm)	Period [1]	Height (cm)	Weight (kg)	Temp. (C) [2]	Heart Rate (bpm) [2]	Systolic Blood Pressure (mmHg) [2]		Diastolic Blood Pressure (mmHg) [2]	
											XX	XX.X	XX	XX
IM HIV- infected	XX-XXX	XXXX	YYYY-MM-DD	XXX	XX:XX	XXXX	XXX	XX	XX.X	XX	XX	XX	XX	XX
		XXXX	YYYY-MM-DD	XXX	XX:XX	XXXX	XXX	XX	XX.X	XX	XX	XX	XX	XX
		XXXX	YYYY-MM-DD	XXX	XX:XX	XXXX	XXX	XX	XX.X	XX	XX	XX	XX	XX
IM HIV- uninfected	XX-XXX	XXXX	YYYY-MM-DD	XXX	XX:XX	XXXX	XXX	XX	XX.X	XX	XX	XX	XX	XX

[1] Period represents the timeframe when the visit took place.

[2] \*Denotes Potentially Clinically Significant Vital Signs outside of these ranges: Temperature: 36.44-37.22 C; Heart Rate: 60-110 bpm; Respiration rate: 12-20 breaths per minute; Blood Pressure: Systolic 100-140 mmHg; Diastolic 60-90 mmHg.

Westat (Created on DDMMYYYY)  
S:\TMB301\ DA\_IM \SAS\L\_VITALS.SAS

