**Table 14.3.3.1**  
**Vital Signs and Changes from Baseline**  
**Safety Population**  
**Weight (kg)**

*Note to programmer: Repeat above for VITAL SIGNS, incrementing x for each new VITAL SIGN (Temperature, Pulse, Respiration Rate, and Blood Pressure). Report only the visits where vital signs were collected, and change "analyte" to "vital sign" in the footnote.*

*Where collected, the pre-dose, post-dose (immediate) and post-dose (15 minutes) values will be presented for each visit. Label visits in the table like this example: Day 15 Pre, Day 15 Post, Day 15 Post 15 min.*

Westat (Created on DDMMYYYY)  
S:\TMB302\ DA\_IM \SAS\t\_vitals1

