**Table 14.3.2.3.3**  
**CD4+ T-Cell Counts (cells/mm^3) and Changes from Baseline**  
**Safety Population - Core HIV-uninfected Group**

		Core HIV-uninfected Group (N=XX)		
		Investigational Period		
		Pre-Steady State + IV Infusions	30 sec IV Push	Follow-up Period
Baseline [1]	N	XX		
	Mean (SD)	XX.X (XX.XX)		
	Median	XX.X		
	25%-75%	XX - XX		
	Min-Max	XX - XX		
Day 15	N	XX		
	Mean (SD)	XX.X (XX.XX)		
	Median	XX.X		
	25%-75%	XX - XX		
	Min-Max	XX - XX		
Change from Baseline	N	XX		
	Mean (SD)	XX.X (XX.XX)		
	Median	XX.X		
	25%-75%	XX - XX		
	Min-Max	XX - XX		
Day 29	N		XX	
	Mean (SD)		XX.X (XX.XX)	
	Median		XX.X	
	25%-75%		XX - XX	
	Min-Max		XX - XX	
...				
...				
End of Study [2]				
...				
Change from Baseline				

N = All subjects in the Safety Population, and denominator for percentage calculations.

[1] Baseline is the last analyte value recorded on Day 1, prior to the first dose administration.

[2] End of Study is Day 99 for subjects in the Sentinel Group and Day 85 for subjects in the Core Group.

Table 14.3.3.1.1.x  
Vital Signs and Changes from Baseline  
Safety Population - xx Group  
Weight (kg)

*Note to programmer: Repeat above for VITAL SIGNS, incrementing x for each new VITAL SIGN (Temperature, Pulse, Respiration Rate, and Blood Pressure). Report only the visits where vital signs were collected, and change "analyte" to "vital sign" in the footnote.*

*Where collected, the pre-dose, post-dose (immediate) and post-dose (15 minutes) values will be presented for each visit. Label visits in the table like this example: Day 15 Pre, Day 15 Post, Day 15 Post 15 min.*

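### The only vital-sign change score planned is from study Baseline; no table summarises the change from pre-dose to post-dose within the same visit, which is the contrast that shows the acute effect of a push or IM dose.

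*SAP*

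**What the plan says.** Protocol 7.1.4 collects a within-visit set of readings around each dose: "Measurements will be taken within 1 hour before the start of the study drug administration and again at both the beginning and end" of the observation period, which lasts 15 minutes for HIV-infected subjects and 60 minutes for volunteers. Protocol 11.5 classes failure to collect vital signs before and after dosing as a violation rather than a deviation.

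For the analysis, section 4.3.4 of the IM SAP and of the IV push SAP use the same sentence: "Actual values and changes from Baseline will be summarized for all visits where collected". Section 3.3.3 of each adds: "Baseline is defined as the last assessment prior to the first dose of study drug", specified as "Day 1 for all HIV infected subjects, Day -55 for HIV uninfected subjects".

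The vital-sign shells (IM Tables 14.3.3.1 and 14.3.3.X, push Table 14.3.3.1.1.x) are titled as values and changes from Baseline and instruct: "Where collected, the pre-dose, post-dose (immediate) and post-dose (15 minutes) values will be presented for each visit". The only end-of-observation label shown is 15 minutes.

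The push shells repeat the layout and footnotes of the laboratory tables. For Core volunteers that footnote reads: "Baseline is the last analyte value recorded on Day 1, prior to the first dose administration". This conflicts with Day -55 in the push SAP's own section 3.3.3.

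IM Listing 16.2.9 and push Listing 16.2.7.2 print readings by visit and scheduled time point. An asterisk "Denotes Potentially Clinically Significant Vital Signs outside of these ranges", for example systolic pressure 100-140 mmHg.

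**The concern.** Safety of the 30-second push and of IM injection is a primary objective, and the protocol takes paired readings around each dose so that acute effects can be seen. The natural contrast is post-dose minus the same visit's pre-dose value. The plan instead measures post-dose readings against a value taken weeks or months earlier, so the change column mixes any acute effect with ordinary variation between visits.

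At stake is how clearly a modest acute haemodynamic effect would show in about 20 subjects per portion, and whether an unusual individual response would appear in any summary.

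**Working it through.** **Inputs.** Baseline days come from section 3.3.3 of each SAP. Push and IM dose days come from Protocol 3.1 and Schedule of Events Tables 1, 3 and 4. For size, the IM SAP says: "Anticipated enrollment in the IM portion is 20 subjects from 4 sites in the United States". The documents give no SD, correlation or power for vital signs, so there is no planned figure to reproduce.

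**1. Age of Baseline at each test-route dose** (dose day minus Baseline day):

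| Group | Baseline day | Dose days | Days since Baseline |
|---|---|---|---|
| IM and Core, HIV-infected | 1 | 29, 43, 57, 71 | 28, 42, 56, 70 |
| Sentinel (push) | 1 | 71, 85 | 70, 84 |
| IM and Core volunteers, SAP text | -55 | 29, 43, 57, 71 | 84, 98, 112, 126 |
| Core volunteers, push shell footnote | 1 | 29, 43, 57, 71 | 28, 42, 56, 70 |

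**2. What the planned tables can and cannot give.** Write B for Baseline. If the same subjects contribute to both rows,

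mean(Post - B) - mean(Pre - B) = mean(Post - Pre),

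so Baseline cancels and the mean acute change is the difference between two printed means. The spread does not follow in the same way:

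Var(Post - Pre) = Var(Post - B) + Var(Pre - B) - 2 Cov(Post - B, Pre - B).

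The covariance is in no planned table, so the SD of the acute change cannot be derived from them. Its minimum and maximum cannot either.

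A hypothetical subject shows the difference. With Baseline 130, pre-dose 112 and post-dose 118 mmHg, the table takes in changes of 112 - 130 = -18 and 118 - 130 = -12. The acute change is 118 - 112 = +6, and no planned table summarises that quantity.

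**3. What the flags catch.** With limits of 100-140 mmHg, a fall from 138 to 102 is 138 - 102 = 36 mmHg, and both readings are unflagged.

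**4. Size of the precision loss (assumed correlations).** If readings share a common SD σ and have correlation ρ, the SD of a change is σ√(2(1 - ρ)). Assume ρ of 0.7 to 0.9 between readings at one visit, and 0.4 to 0.7 between a reading and study Baseline.

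- Same-visit change: σ√(2 × 0.1) = 0.45σ to σ√(2 × 0.3) = 0.77σ.
- Change from study Baseline: σ√(2 × 0.3) = 0.77σ to σ√(2 × 0.6) = 1.10σ.
- Ratio of the two SDs: √(0.3/0.3) = 1.0 to √(0.6/0.1) = 2.4.

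As a yardstick only, since no vital-sign test is planned, the mean shift detectable with n = 20 at two-sided 5% and 80% power is (1.96 + 0.84) × SD/√20. That is 0.28σ to 0.48σ for the same-visit change and 0.48σ to 0.69σ for change from study Baseline.

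**The case against.** The strongest answer is that nothing is lost, only left uncomputed. The pre-dose and post-dose actual values sit side by side for each visit, so the mean acute shift is visible. Both listings print every reading by time point, and with about 20 subjects per portion each individual change is a subtraction between neighbouring lines. Acute reactions also have their own route. The Schedule of Events sends abnormalities seen during observation to the AE form, Protocol 8.5 grades infusion reactions and anaphylaxis, Protocol 4.3 links them to the DLT rules and DMC review, and adverse events are tabulated by administration period. The SAPs describe the analysis as primarily descriptive.

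Most of this stands, and it limits the point. A reader might infer that the acute effect is hidden or that individual falls cannot be recovered. The side-by-side rows and the listings rule that out. A reader might also infer that no dose is ever compared with its own pre-dose value. At the first study dose Baseline will normally be that visit's pre-dose reading, although that dose is always an infusion and never a push or IM dose.

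One can also assume SDs in mmHg and work out how often a 20 mmHg fall would be missed or wrongly suggested. Those rates would rest on SDs the documents do not give and on cut-offs neither SAP plans, so they do not describe the planned analysis.

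The answer does not remove the gap. Rebuilding the paired change by hand from a listing is not a planned summary, fixed-range flags do not detect a large change inside the range, and adverse event reporting does not describe the distribution of acute changes.

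**Conclusion.** The point holds as a limited one. Both SAPs plan a single vital-sign change score and apply it to post-dose readings, with a reference 28 to 84 days old in HIV-infected subjects and, by the SAP text, 84 to 126 days old in volunteers. The volunteer range is not uniform across the documents, because the push shells' Day 1 footnote would make it 28 to 70 days for Core volunteers. The within-subject acute change, its SD and its extremes appear in no planned table.

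The cost in precision cannot be read from the documents. Under the assumed correlations the SD ratio is about 1.0 to 2.4, so the loss could be nil or substantial. The documents do not support a conclusion that the primary safety assessment fails. They support adding a better-targeted summary of data already collected.

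**What to change.** In section 4.3.4 of both SAPs, and in IM shells 14.3.3.1 and 14.3.3.X and push shell 14.3.3.1.1.x:

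- Add change from the same visit's pre-dose value at each post-dose time point, summarised by route with n, mean, SD, median, minimum and maximum. State whether n counts subjects or doses where several doses by one route are pooled.
- Keep change from study Baseline for longer-term trend.
- Label the volunteers' end-of-observation row as 60 minutes, to match Protocol 7.1.4.
- Reconcile the Day 1 Baseline footnote in the push volunteer shells with Day -55 in section 3.3.3.

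The cost is SAP and shell wording and one derived variable. Both readings of the pair are already required at each dose.
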